1. STUDY OBJECTIVES

1.1 **Primary Study Aims:** Determine the feasibility of an integrated psychosocial treatment (ACT + MBRP) in veterans with chronic pain with evidence of opioid-related problems. Chronic pain patients ($n = 120$) who are receiving opioid therapy and who are identified as opioid misusing, abusing, or dependent will be recruited from the Albuquerque Veterans Administration (VA) Hospital. Participants will be randomized to receive standard care or standard care in addition to ACT+MBRP. **Hypothesis 1: Feasibility of recruitment:** Given the high prevalence of both chronic pain and opioid-related problems in VA populations, we hypothesize it will be possible to recruit our target sample size ($n = 120$) within a 15-18 month timeframe. **Hypothesis 2: Feasibility of retention:** Drop-out rates will be consistent with other trials of similar psychosocial interventions for chronic pain (i.e., < 20%^{5,21-23}).

1.2 **Secondary Study Aims:** To examine weekly progress on specific therapy targets (e.g., pain acceptance, self-compassion, opioid craving) in the interventions in order to identify potential mechanisms of change and to identify the choice of intermediate endpoints for a larger randomized clinical trial.

Hypothesis 1: Evidence of treatment mechanisms: The combined ACT+MBRP treatments will be associated with changes in treatment mechanisms specified within the therapeutic models and in a manner consistent with that of previous work on ACT and MBRP, in comparison with standard care.

Hypothesis 2: Selection of intermediate endpoints: Weekly progress measures will provide data indicating measures of treatment-specific mechanisms that are most sensitive to change. We hypothesize that acceptance of pain discomfort will be most sensitive to change in ACT and that reductions in reactivity to substance craving will be most sensitive to change in MBRP.

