9.2 Sample Size and Randomization

Commented [KV4]: Blocking

Statistical Power for Secondary Aims: We estimated statistical power for the mediation analyses using parameter estimates from prior studies of mediation following ACT for chronic pain⁵ and following MBRP for substance use disorders^{7,63} to estimate the effect sizes for the behavioral measures in the current study. Following ACT, numerous behavioral measures significantly mediated changes in disability, depression, pain-related anxiety, medical visits, and number of classes of prescribed analgesics, with large mediation effect sizes. The prior studies of MBRP have found that experiential avoidance, awareness, and nonjudgment significantly mediated the association between treatment and changes in craving ($\alpha = 0.56$; $\beta = -0.43$) and that craving significantly mediated the association between treatment and changes in substance use ($\alpha = -0.20$; $\beta = 0.71$). Based on these effect sizes and power estimates for testing mediation derived from a simulation study⁷¹, we will have power greater than 0.80 to detect significant mediating effects with the proposed sample size of 120.

Examining mechanisms of change assumes that treatment influences change in the clinical outcome measures at follow-up, thus we also estimated the power to detect a main effect of treatment on the clinical outcome measures. Effect size estimates were drawn from prior studies of ACT for patients with chronic pain^{5,23,60,72} and MBRP for substance use disorders^{52,63,73}. The effect sizes for ACT in comparison to treatment as usual or active treatment for chronic pain have ranged from 0.29 to 1.09. The effect sizes for MBRP in comparison to treatment as usual for substance use and craving have ranged from 0.21 to 0.52. Based on these studies, we estimate a minimum average effect size of $d=0.25$. Using a mixed-effects linear model with $\alpha=0.05$ (two-tailed test), three repeated assessments (baseline, end of treatment, 6-month follow-up), and a correlation among repeated measures of 0.43 (based on prior studies) we will need 60 subjects per condition (total $n = 120$) for 80% power to detect a main effect of ACT+MBRP in comparison to standard care.

Treatment Assignment Procedures

We will use a random order variable-sized block randomization procedure with block sizes of 2, 4, and 6. The investigators will be blind to the size of each block and randomization allocation.

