9.5.1 Primary Outcome

The outcome for Aim 1 will be descriptive, including calculating the percent of individuals enrolled in the study versus those eligible and the percent of individuals who remain in the study. We will pay particular attention to issues of retention, as the treatment program will occur over 12 weeks and this length may impact treatment completion (previous programs of ACT alone, which have lasted eight weeks, have had drop-outs of < 20%^{17,21}. The assessment of this latter primary outcome will occur at each treatment meeting (as this is the only way to assess retention) and follow-up.

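### The stated 80% power for a treatment main effect of d = 0.25 with 60 per condition does not follow from its inputs; the main effect as written has about 41%

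*Combined protocol and SAP*

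**What the plan says.** Section 9.2 (Sample Size and Randomization), under power for the secondary aims, bases its effect size on earlier ACT trials (0.29 to 1.09) and MBRP trials: "The effect sizes for MBRP in comparison to treatment as usual for substance use and craving have ranged from 0.21 to 0.52". From these, "we estimate a minimum average effect size of $d=0.25". The calculation is then set out as "Using a mixed-effects linear model with $\alpha=0.05$ (two-tailed test"), with "three repeated assessments (baseline, end of treatment, 6-month follow-up") "and a correlation among repeated measures of 0.43 (based on prior studies"). The conclusion is that "we will need 60 subjects per condition (total $n = 120$) for 80% power to detect a main effect of ACT+MBRP" relative to standard care.

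The section names no formula, software or contrast, gives no conversion of d to another effect-size scale, and makes no allowance for drop-out. The sentence introducing the calculation ties it to the premise that treatment changes the clinical outcomes at follow-up, on which the mediation analyses depend. Section 9.1 specifies those analyses on the 6-month outcomes, adjusted for baseline.

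The primary aim does not use this calculation. Section 9.5.1 states: "The outcome for Aim 1 will be descriptive, including calculating the percent of individuals enrolled in the study versus those eligible".

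**The concern.** A standardised difference of 0.25 is small, and 60 per condition is a modest sample. Averaging three assessments correlated at 0.43 reduces the variance only to 0.62 of that of a single assessment, which is too little to bring power to 80%.

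The power figure is offered as support for the premise of the mechanism analyses. If the true effect is the plan's own minimum, the main effect as described would be non-significant in about 59% of trials, not 20%. A reader relying on the 80% could take a null result as evidence against the treatment when planning the larger trial.

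**Working it through.** **Inputs, all from section 9.2:** d = 0.25, two-sided alpha 0.05, three assessments, correlation r = 0.43, 60 per condition. **Assumed, because the plan does not say:** SD 1 at each visit, the same correlation between every pair of visits, complete data, no clustering by therapy group.

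**Formula.** For a contrast with per-person variance v, SE = √(2v/60) and power ≈ Φ(d/SE − 1.96). The normal approximation is used; the noncentral t lowers power by at most 0.006.

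**The main effect as written (mean of three assessments).** v = (1 + 2 × 0.43)/3 = 0.620; SE = √(2 × 0.620/60) = 0.144; d/SE = 1.74; power = 0.413. A simulation of 20,000 trials gave 0.409. Reaching 80% needs 2 × 0.620 × (1.96 + 0.842)²/0.25² = 156 per condition.

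**Other contrasts, each taking d = 0.25 as the difference on that contrast:**

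| Contrast | v | Power |
|---|---|---|
| Mean of two later visits, baseline-adjusted | (1 + 0.43)/2 − 0.43² = 0.530 | 47% |
| Mean of two later visits, unadjusted | (1 + 0.43)/2 = 0.715 | 37% |
| 6-month outcome, baseline-adjusted | 1 − 0.43² = 0.815 | 33% |
| Mean of two later visits minus baseline | 0.715 + 1 − 2 × 0.43 = 0.855 | 32% |
| One later visit, unadjusted | 1 | 28% |
| Change to one later visit | 2 × (1 − 0.43) = 1.14 | 25% |

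**Could the correlation explain the gap?** No. At r = 0 the three-assessment mean has v = 0.333 and power 66%.

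**Where d sits matters.** Baseline precedes treatment, so its expected difference is zero. A difference of 0.25 in the three-assessment mean therefore needs 0.25 × 3/2 = 0.375 SD at both later visits. If the difference is 0.25 SD at the later visits only, the mean difference is 0.5/3 = 0.167 and power is about 21%.

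**Attempt to reproduce N = 120.**

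- Between-group F test, f = d/2 = 0.125: λ = 0.125² × 120 × 3/(1 + 2 × 0.43) = 3.02 on 1 and 118 df; power 0.407; 80% needs N = 314.
- Group-by-time F test, f = 0.125: λ = 0.125² × 120 × 3/(1 − 0.43) = 9.87 on 2 and 236 df; power 0.805. N = 118 gives 0.798, so 120 is the smallest even N that reaches 80%.

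The second calculation matches the plan's number, but f = d/2 does not carry over to an interaction. Group differences of (0, 0.25, 0.25) SD give an interaction f of 0.059 and power 24%; linear growth to 0.25 gives f = 0.051 and 19%. To reach f = 0.125 takes about 0.53 SD at both later visits, or about 0.61 SD at the last visit under linear growth.

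**What 60 per condition can support:**

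| Contrast | d at 80% power, 60 per condition | d at 80% power, 48 per condition | n per condition for d = 0.25 | Power at d = 0.40, 60 per condition |
|---|---|---|---|---|
| Mean of three assessments | 0.40 | 0.45 | 156 | 79% |
| Two later visits, baseline-adjusted | 0.37 | 0.42 | 134 | 85% |
| 6-month, baseline-adjusted | 0.46 | 0.52 | 205 | 68% |

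The 48 column assumes that 20% contribute no data (60 × 0.8 = 48), the upper end of the drop-out hypothesis in section 1.1.

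**The case against.** The strongest reply is that N = 120 is not arbitrary: a standard group-by-time calculation reproduces it, so the fault may be a mislabelled test and an invalid effect-size conversion rather than arithmetic. That is plausible, though it is an inference, since the plan names no method. It does not rescue the sentence, which claims a main effect at d = 0.25; on the group-by-time test that effect has only about 19% to 24% power.

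A second point is that a mean including baseline is not the contrast closest to the planned analysis. Section 9.1 uses 6-month outcomes adjusted for baseline, for which power is 33% and the detectable d is 0.46. This is fair. The 41% leads here only because main effect is the plan's own term, and the closer contrast is less favourable.

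Third, the 25% to 47% range holds only when d = 0.25 is defined separately on each contrast and the omnibus interaction is left out. That is correct, and the 19% to 24% figures lie below it.

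Fourth, the 48-per-condition figures are a worst case. Drop-out is hypothesised below 20%, some who leave treatment will still be assessed, and maximum likelihood uses partial data.

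Finally, section 9.1 lists no stand-alone test of treatment on the clinical outcomes, and the mediation power statement is separate and not questioned here. This limits the consequence but does not make the 80% correct.

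**Conclusion.** The concern holds. At d = 0.25, power for the main effect as written is about 41%, not 80%, and about 25% to 47% across the contrasts tabulated. No treatment contrast examined reaches 80% with a true difference of 0.25. The result rests on equal variances, a common correlation of 0.43 and complete data; drop-out or clustering within therapy groups would lower power further.

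The statement should be corrected, but its reach is limited to the secondary aims. The descriptive primary aim and the recruitment target of 120 stand. The sample still has about 80% power for d near 0.40 on the three-assessment mean, a value inside both effect-size ranges quoted in section 9.2.

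**What to change.** Keep n = 120 as the feasibility target. In section 9.2, name the test and contrast, define d on that contrast (stating whether baseline is included), and replace the 80% statement. For example:

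*With 60 per condition, two-sided alpha 0.05 and a correlation of 0.43, power for the main effect averaged over the three assessments is about 41% at d = 0.25; 80% power is reached at d of about 0.40 (0.45 if 20% per condition provide no data).*

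If another contrast is chosen, the detectable d is about 0.37 (0.42) for the baseline-adjusted mean of the two later visits, or 0.46 (0.52) for the baseline-adjusted 6-month outcome, the one closest to section 9.1. If a group-by-time test was intended, say so and give the effect as f = 0.125 with the pattern it implies (about 0.53 SD at both later visits, or about 0.61 SD at the last visit under linear growth), not as d = 0.25.

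The cost is rewording one section and a less favourable stated power for the secondary aims. No participants are added and the primary aim does not change.

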Objectives: Determine the feasibility and acceptability of a combined treatment for veterans with comorbid chronic pain and opioid misuse or dependence, as well as assess mechanisms of change during the combined intervention. A secondary objective is to examine weekly progress on specific therapy targets (e.g., pain acceptance, self-compassion, opioid craving) in the interventions in order to identify potential mechanisms of change and to identify the choice of intermediate endpoints for a larger randomized clinical trial. **Approach**—To test the feasibility of recruitment and retention, as well as study weekly progress on treatment targets, within a randomized clinical trial (RCT) of Acceptance and Commitment Therapy (ACT) + Mindfulness-Based Relapse Prevention (MBRP) or treatment as usual for chronic pain and opiate misuse.

Design and Outcomes: Veterans with chronic pain and opiate misuse, abuse, or dependence who are receiving long-term opioid therapy (i.e., 90+ days) will be recruited from the Raymond G Murphy Veterans Affairs (VA) Medical Center in Albuquerque, NM. Treatment will begin in Year 1 and conclude in Year 2 with follow-up assessment lasting through the first quarter of Year 3. At the time of enrolling in the trial, individuals will participate in a baseline assessment including self-report and behavioral measures. Participants ($n = 120$) will then be randomized to one of two treatment conditions: (1) treatment services-as-usual (i.e., standard care) or (2) standard care with eight weeks of group ACT plus four weeks of group MBRP. Participants will complete assessments at baseline (entry into the study), weekly during the first three months of the study (during treatment), three months after entry in the study (end of treatment), and nine months after entry in the study (six months after treatment conclusion).

Self-Report and Behavioral Assessment Batteries—Self-report and behavioral assessments will be used to evaluate study hypotheses. For the follow-up assessments we will use contact information collected at baseline to contact participants by phone one week prior to their scheduled follow-up date.

Participants will be reminded about procedures and scheduled to complete all assessments at the VA.

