6.2.5.1 Participant Compensation

Remuneration for each of the assessments is as follows: Participants will receive \$60 for completion of the baseline session, \$5 per week for completing weekly assessments during active treatment (\$60 total), \$50 for completing the end of treatment assessment (week 13), and \$50 for completing the six-month follow-up (week 37), totaling \$220. Individuals who complete all assessments will be given a \$50 bonus at the 6-month follow-up, for a maximum compensation of \$270.

Participant costs per year are as follows:

Year 1: \$9,680	(64 baseline, 64 X \$60=\$3840; 64 weekly treatment, 64 X \$60=\$3840; 40 post-treatment; 40 X \$50=\$2000).
Year 2: \$19,520	(56 baseline, 56 X \$60=\$3360; 56 weekly treatment, 56 x \$60= \$3360; 80 post-treatment, 80 X \$50=\$4000; 88 six month follow-up, 88 X \$50=\$4400; 88 bonus six month maximum completion, 88 X \$50=\$4400).
Year 3: \$3,200	(32 six month follow-up, 32 X \$50=\$1600; 32 bonus six month maximum completion, 32 X \$50=\$1600).

The participant compensation record is displayed in Appendix VI.

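### Section 9.2 claims 80% power at exactly the number randomised, with no allowance for missing outcome assessments, although the plan hypothesises drop-out of up to 20%

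*Combined protocol and SAP*

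**What the plan says.** The power statement for the clinical outcomes in Section 9.2 lists its inputs. The effect is given as "we estimate a minimum average effect size of $d=0.25". The method is described as "Using a mixed-effects linear model with $\alpha=0.05$ (two-tailed test", with "three repeated assessments (baseline, end of treatment, 6-month follow-up", and a correlation of 0.43 between assessments. The conclusion is "we will need 60 subjects per condition (total $n = 120$) for 80% power to detect a main effect of ACT+MBRP". For mediation, the same section says "we will have power greater than 0.80 to detect significant mediating effects with the proposed sample size of 120".

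The synopsis and Section 3 set the number randomised: "Participants ($n = 120$) will then be randomized to one of two treatment conditions". Hypothesis 2 in Section 1.1 reads "Drop-out rates will be consistent with other trials of similar psychosocial interventions for chronic pain (i.e., < 20" (a percentage).

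Section 9.1 distinguishes people who leave treatment but continue with assessments from people who stop the research assessments, with or without leaving treatment. It plans maximum likelihood estimation on all available data. Section 9.2 mentions neither attrition nor any inflation of the sample size.

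**The concern.** A calculation that yields 60 per condition with three assessments each describes 60 people with complete data. Here it is also the number enrolled, so the two agree only if nobody misses an outcome assessment. The plan does not expect that: retention is one of its two primary hypotheses, and Section 9.1 notes that a 12-week programme may affect completion.

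At stake is how the Aim 2 results are read. A null treatment effect on the clinical outcomes would be judged against 80% power that the design does not have once outcome data are lost. Aim 2 is also meant to inform the larger trial.

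**Working it through.** **Inputs (Section 9.2 unless noted).** d = 0.25; two-sided alpha 0.05; m = 3 assessments; correlation rho = 0.43; 60 per condition, N = 120; drop-out below 20% (Section 1.1). Assumed here: SD 1, the same correlation between every pair of assessments, and equal loss in both arms.

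**1. Reproducing the plan's figure.** The document does not name its formula. A repeated-measures group-by-time F test does return 120:

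- f = d/2 = 0.125
- lambda = f² × N × m / (1 − rho) = 0.015625 × 120 × 3 / 0.57 = 9.87
- degrees of freedom 2 and 2(N − 2) = 236; power = 0.805

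This is the smallest even N that reaches 0.80.

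**2. Same test, completers only.**

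| Loss of outcome data | Complete cases | lambda | Power |
|---|---|---|---|
| 0% | 120 | 9.87 | 0.805 |
| one per arm | 118 | 9.70 | 0.798 |
| 10% | 108 | 8.88 | 0.759 |
| 20% | 96 | 7.89 | 0.704 |

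Drop-out strictly below 20% means at most 23 of 120 lost, so at least 97 remain. Power at 97 is 0.709.

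**3. A check that does not depend on the formula.** Take the 80% at 120 as given. The noncentrality is 1.960 + 0.842 = 2.80 and scales with the square root of the information.

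- 10% loss: 2.80 × √0.9 = 2.66; power 0.757
- 20% loss: 2.80 × √0.8 = 2.51; power 0.707

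**4. Crediting maximum likelihood on all available data.** The expected information of the three-time model was computed with 20% lost in each arm, for three shapes of treatment effect (baseline, Week 13, 6 months), each scaled to f = 0.125. A chi-square approximation gives 0.81 with complete data.

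| Effect shape | All lost before Week 13 | Half before, half after | All lost after Week 13 |
|---|---|---|---|
| Linear (0, 0.5, 1) | 0.739 | 0.744 | 0.748 |
| Step (0, 1, 1) | 0.748 | 0.771 | 0.791 |
| Late (0, 0, 1) | 0.721 | 0.722 | 0.724 |

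The range is 0.72 to 0.79, and every pattern tried is below 0.80.

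**5. Effect detectable with 80% power.** At face value, 0.25/√0.9 = 0.26 at 10% loss and 0.25/√0.8 = 0.28 at 20% loss, on completers.

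**6. Mediation.** The quoted pair (0.56, −0.43) was simulated with a joint-significance test, 4,000 runs. If 0.56 is a difference in SD units, power is about 0.86 at 120 and 0.77 at 96. If both are standardised coefficients, it is about 0.98 at 120 and 0.96 at 96. The document does not say which reading applies.

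**The case against.** **Drop-out from treatment is not loss of outcome data.** This stands, and it limits the size of the point. Section 9.1 separates the two. Sections 5.4 and 8 keep non-attenders in the study, and Section 6.2.5.1 pays for assessments with a completion bonus. A reader might infer that Hypothesis 2 makes 96 the number expected to supply 6-month data. The documents do not say so: 96 is the outer edge, reached only if every drop-out also stops assessments. If the 20% applied only to the group programme, one arm would be exposed. Losing 12 of its 60 leaves an information ratio of 2 × 60 × 48 / (60 + 48) / 60 = 0.889, and 2.80 × √0.889 = 2.64 gives power of about 0.75. Even so, Section 9.1 defines two categories that do not complete research assessments, and Section 9.2 allows for neither.

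**Maximum likelihood uses partial records.** It does, and step 4 credits it. It narrows the gap without closing it, and it is an analysis method, not a sample-size allowance.

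**The practical effect is small.** A detectable effect of 0.28 is still below the smallest ACT effect cited (0.29), though above the bottom of the MBRP range (0.21). The trial is a feasibility study with a descriptive primary aim. Sensitivity to change is judged by the slopes of the weekly measures, so the choice of intermediate endpoints rests only partly on the 6-month results. This makes the point modest. It does not make the stated 80% correct.

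**The budget.** A reader might take the 88 Year 2 six-month visits plus the Year 3 line ("32 six month follow-up, 32 X \$50=\$1600"), which total 88 + 32 = 120, as proof that zero loss was assumed. The lines may equally be a spending ceiling, so nothing is built on them.

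**Conclusion.** The point holds for the treatment effect on clinical outcomes. The stated 80% is a complete-data figure with no margin. On the plan's own inputs the shortfall at 20% loss of outcome data is about 1 to 10 percentage points: about 0.70 on completers and 0.72 to 0.79 with maximum likelihood. At 10% loss, completer power is about 0.76. These figures rest on the group-by-time reproduction, a common correlation of 0.43 and equal loss in both arms.

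Two stronger readings are not supported. The first is that the mediation power also fails. The plan claims more than 0.80 there, and whether 96 participants fall short depends on a scale for the coefficients that the document does not give. The second is that attrition brings power down to about a third. A literal between-group main effect averaged over the three assessments has power of about 0.41 at 60 per arm and 0.34 at 48. Most of that gap comes from which test the 120 belongs to, which is a separate question from missing data.

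**What to change.** Keep enrolment at 120. In Section 9.2:

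- State an assumed rate of missing 6-month assessments, kept distinct from leaving treatment; 10% and 20% would serve as examples.
- Replace the 80% claim with the power at those rates, or with the effect detectable with 80% power (about d = 0.26 and 0.28 on the present calculation), computed for the same test that the analysis will use.
- Restate the mediation power at the reduced numbers, and say whether the quoted coefficients are SD differences or standardised.

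The cost is a short recalculation, a few sentences and a slightly less favourable stated figure. No additional participants are needed and the design does not change.
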